5.5 HANDLING OF MISSING DATA AND/OR INVALID DATA AND OUTLIERS

5.5.1 Efficacy

In case of missing data, the following rules will be applied as a primary imputation method applicable to all visits of interest (follow-up study time points 2, 2.5, 3, 4 and 5 years):

For all analysis timepoints, a review of the visits with available BCVA value will be done by GenSight to decide, for each patient, which visit will be used for this specific timepoint analysis. The document will be provided in excel format, and then imported in SAS in order for the statistician to perform the analysis (CLIN-06_DRM_Listings_V1.0_30JUN2022).

If Year-2 visit is not available at Clin06 inclusion, then “Follow-up Visit 12” (corresponding to Week 96) from Clin03A/Clin03B will be used.

After this affectation, in case of missing LogMAR value at a visit, LOCF will be applied with all analysed visits.

When a test result score/value for the Pelli-Robson Contrast test is missing at any visit for the reason that the subject was unable to perform because the vision was too poor, the following convention will be used: the worst possible score for the given test will be assigned as the value for that visit (i.e., 0 LogCS).

The imputation method of missing data used in each analysis will be specified in the TFLs in a footnote.

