7. INVESTIGATIONAL PLAN

7.1 Overall Study Design and Plan

This study will be a multinational multicenter prospective non-interventional long-term follow-up clinical study of subjects previously treated with GS010 in either the RESCUE or REVERSE studies. Of the 7 investigational centers participating, 4 are located in Europe (1 each in France, Germany, Italy, and the United Kingdom,) and 3 are located in the United States.

[figure not shown]
Subjects will be enrolled in the long-term follow-up study when informed consent is provided and inclusion/exclusion criteria are met. Enrollment will occur during the Inclusion Period, which will be during the RESCUE and REVERSE study Week 96/End-of-Study (EOS) Visit or anytime up to 1 day prior to the long-term follow-up study Visit 2 (Day 180). Preferably, the assessments required to be performed during the Inclusion Period will be conducted at the RESCUE and REVERSE study Week 96/EOS visit; however, if the subject cannot undergo all assessments at that time, the assessments may be performed at a later date during the Inclusion Period, but no later than one day before the Year 2.5 visit (Day 180).

The study population will be limited to the number of subjects treated in the RESCUE and REVERSE studies. The total length of the long-term follow-up study will be 3 years and the total length of the subject follow-up from IMP administration will be 5 years. The RESCUE and REVERSE long-term follow-up study is planned to start towards the end of 2017 and study start will be defined as the first subject's first visit in this study. The approximate study end date is planned to be towards the end of year 2022 after the last subject's last visit.

The follow-up will include onsite assessments of safety, QOL, and efficacy as in the RESCUE and REVERSE studies. The study will include 5 follow-up study visits: at 2.0-, 2.5-, 3-, 4-, and 5 years post-treatment.

Statistical analysis of the data will include descriptive summaries of safety, QOL assessments, and statistical testing of efficacy endpoints.

Figure 1: Study Design Schematic of the Long-term Follow-up of Subjects from the RESCUE and REVERSE Clinical Studies

Note: Inclusion into the long-term follow-up study will be allowed from W96 up to 1 day prior to Y2.5.

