11.2 Statistical Analysis Plan

A statistical analysis plan (SAP) will be prepared after the protocol is approved and before database lock occurs. The SAP will provide further details regarding the endpoints, data handling rules, and the statistical methods to be used to address all study objectives and endpoints. The SAP will also include display formats for the summary and analysis tables, listings, and graphical displays.

Data for quantitative variables will be presented by arithmetic mean (for other continuous variables), standard deviation (SD) median, first quartile (Q1), third quartile (Q3), minimum and maximum. Data for categorical and binary variables (responder analysis) will be presented by counts and percentages. Least square means, 95% confidence interval (CI) and P-values will be reported derived from models and statistical tests.

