11.5.2.2 LogMAR

Analysis for European Medicines Agency

The primary analysis will be performed on the intent-to-treat (ITT) population. The change from baseline to each follow-up visit in the LogMAR acuity will be the response. The change from baseline of all-GS010 eyes will be compared to the change from baseline of all-sham eyes (intra-subject comparison) using a mixed-effects ANCOVA model using the following terms (or covariate) in the model:

- Subject and eyes of the subject as random factors
- The baseline LogMAR
- Treatment

The investigative site will not be included in this analysis as the number of subjects recruited per site will be very small. However, stratification by geographical area will be performed as a sensitivity analysis. Neighboring countries can be pooled to reach at least 9 subjects per geographical entity. The analysis will be performed based on alpha of 0.05 (two-sided test).

An additional model will add the treatment by geographical interaction to investigate lack of generalizability of the treatment effect.

Analysis for Food and Drug Administration

The primary analysis will be performed on the ITT population. The change from baseline of the best-GS010 treated eyes will be compared to the change from baseline of the best-sham eyes (inter-subject comparison) using an ANCOVA with baseline LogMAR as covariate. The analysis will be performed using an alpha of 0.05 (two-sided test). The statistical significance in favor of the best-GS010 treated eyes against the best-sham eyes will show evidence of the advantage of using GS010 for halting visual acuity loss or improving visual acuity in subjects with LHON. The difference in the mean change from baseline (adjusted mean difference) between the two treatment groups and associated 95% confidence interval will be reported.

The center will not be included in the analysis as the number of subjects recruited per site will be very small. However, stratification by geographical area will be performed as a sensitivity analysis. Neighboring countries can be pooled together to reach at least 9 subjects per geographical entity. The pooling of countries will be performed during the masked review of data.

An additional model will add the treatment by geographical area interaction to test for a lack of generalizability of the treatment effect.

The same analysis will be repeated for worst-GS010 treated eyes against worst-sham eyes.

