11.5.7 Interim Analyses

Two interim statistical analyses are planned at completion of Visit 3 (Year 3) and Visit 4 (Year 4), in addition to the final analysis at Year 5 in the Clinical Study Report.

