3.5 MASKING

No investigational product will be administered during this long-term follow-up study. Unmasking procedures are not pertinent to this study as no study treatment/study procedures will be performed during the long-term follow-up.

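### SAP 5.5.1 lets the sponsor choose, patient by patient, which BCVA visit stands for each time point, with no visible selection rule and no stated masking of the reviewers

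*SAP*

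**What the plan says.** SAP 5.5.1 opens its efficacy rules with "In case of missing data, the following rules will be applied as a primary imputation method", for all follow-up time points from Year 2 to Year 5. The first step is the sponsor's review: "a review of the visits with available BCVA value will be done by GenSight to decide, for each patient, which visit will be used". The outcome is recorded in a spreadsheet, named in the SAP as a data-review listing, version 1.0, dated 30 June 2022, and imported into SAS. SAP Final Version 2.0 carries the same date.

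One assignment is fixed: if there is no Year 2 visit at inclusion, the parent study's Week 96 visit is used. The last step is "After this affectation, in case of missing LogMAR value at a visit, LOCF will be applied with all analysed visits".

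Protocol 11.2 had promised that "The SAP will provide further details regarding the endpoints, data handling rules, and the statistical methods" would follow. On masking, SAP 3.5 says only that "Unmasking procedures are not pertinent to this study". The one masked data review mentioned in either document is in Protocol 11.5.2.2, and it concerns geography: "The pooling of countries will be performed during the masked review of data".

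**The concern.** The review works from visits that already have an acuity value, and it settles which value enters the analysis. Without a written criterion, the analysed LogMAR can depend on the acuity itself and, if eye allocation is known, on which eye looks better. LOCF does not protect against this, because it acts only on what the review leaves missing.

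Competing values can arise. Protocol 8.8 allows unscheduled visits at any time, with vision assessments where judged appropriate. Protocol 8.7 gives an early termination visit the full end-of-study assessments. A scheduled visit may also fall outside its plus or minus 4 weeks.

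At stake are the EMA all-eyes comparison, the FDA best-eye comparison (each tested at two-sided 0.05 in SAP 8.5.2.2) and the BCVA responder tables in SAP 8.5.2.4. The primary endpoint, related adverse events, is untouched.

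**Working it through.** **Step 1: is there a rule or a masked reviewer elsewhere in the visible text?**

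| Place | What it covers | Fills the gap? |
|---|---|---|
| SAP 3.2, Table 1 | Plus or minus 4 weeks for Visits 2 to 5 | No: scheduling window, not a selection rule |
| SAP 6.3 | Allowable window, including unscheduled visits | No: defines per-protocol membership |
| SAP 3.1 | Parent-study masking of subjects, follow-up team and reading lab | No: sponsor reviewers not mentioned |
| SAP 3.5 | Unmasking procedures | No: silent on data reviewers |
| SAP 8.2 | Data review meeting decides major deviations | No: masking not stated |
| Protocol 11.5.2.2 | Masked review for pooling countries | No: not linked to visit choice |
| SAP 8.8 | Changes from the protocol | No: visit review not listed |

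By contrast, SAP 5.5.2 gives step-by-step deterministic rules for partial adverse event dates.

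**Step 2: how much could it matter?** The plan gives no figure to reproduce. The documents supply only alpha = 0.05 (two-sided) and 0.1 LogMAR = 5 letters, that is, 50 letters per LogMAR. The rest is assumed:

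- n = 30, 60 or 76
- share f of patients with two candidate visits: 10% or 25%
- visit noise as a share v of per-eye variance: 0.10 to 0.50
- no true effect, normal values, stable changes of the two eyes uncorrelated
- one visit serves both eyes, and the candidate with the lower GS010-minus-sham LogMAR is always taken

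*Mean bias.* The better of two exchangeable normal values lies 0.564 SD from the mean, and the between-eye difference has noise SD x sqrt(2). So bias = f x 0.564 x SD x sqrt(2), the same for both contrasts. For a per-eye visit SD of 0.10 to 0.20 LogMAR:

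- f = 10%: 0.10 x 0.564 x 0.10 x 1.414 = 0.008, and with SD 0.20, 0.016 (0.4 to 0.8 letters)
- f = 25%: 0.020 to 0.040 (1 to 2 letters)

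*Type I error, worst assumed cell* (n = 76, f = 25%, v = 0.50, per-eye SD set to 1, so noise SD 0.707):

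- bias = 0.25 x 0.564 x 0.707 x 1.414 = 0.141
- EMA, paired: SE = sqrt(2/76) = 0.162; 0.141/0.162 = 0.87; P(Z > 1.96 - 0.87) + P(Z < -1.96 - 0.87) = 0.140
- FDA, 38 best eyes per arm: SE = sqrt(4/76) = 0.229; 0.141/0.229 = 0.615; the same formula gives 0.094

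Simulation with 60,000 replicates per cell (paired t-test for EMA, two-sample t-test for FDA) gives, at v = 0.50:

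| n | 10% with a choice, EMA / FDA | 25% with a choice, EMA / FDA |
|---|---|---|
| 30 | 0.056 / 0.053 | 0.085 / 0.067 |
| 60 | 0.059 / 0.055 | 0.118 / 0.085 |
| 76 | 0.065 / 0.059 | 0.139 / 0.094 |

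Over all assumed n and noise levels, the ranges are 0.050 to 0.065 (EMA) and 0.050 to 0.059 (FDA) at 10%, and 0.055 to 0.139 and 0.054 to 0.094 at 25%. A value-blind pick at 25% gives 0.049 to 0.051 throughout.

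*Sensitivity.* If the choice is made on the FDA-analysed eye instead, the worst cell becomes 0.092 (EMA) and 0.138 (FDA), so the two maxima cannot both apply. A second set of assumptions (n = 30 or 60, correlation 0.7 or 0.9 between candidates, each contrast favoured separately) gives 0.049 to 0.056 at 10% and 0.056 to 0.091 at 25%. If half the patients had a choice, it gives 0.076 to 0.220.

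**The case against.** **The rule may exist out of sight.** Some SAP text between 5.5.2 and Section 6, and the mapping file itself, were not available to this review. The heading of 5.5 also promises handling of invalid data and outliers, which the visible subsections do not cover. This stands, and it limits the claim to the visible text.

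**The process is partly fixed.** The mapping is a named, versioned file with the same date as the SAP, and Year 2 has its own fallback. The opening words "In case of missing data, the following rules will be applied as a primary imputation method" may confine the review to patients whose scheduled value is missing, although the review sentence itself covers all time points and each patient. This also stands, but a fixed date supplies neither a criterion nor masking.

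**The size is a constructed worst case.** Nothing suggests that reviewers favour GS010, and n, the share with a choice and the noise are not in the documents. The t-tests leave out baseline adjustment and the fixed off-chart LogMAR codes of SAP 5.4, and the responder tables are not quantified. This is accepted: the figures are illustrations only.

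**Efficacy is secondary and has other checks.** SAP 8.5.4 applies no multiplicity adjustment. SAP 8.5 repeats every efficacy analysis in the per-protocol set, SAP 8.1 reports missing acuity data, and footnotes will state the imputation used. These are partial safeguards: the per-protocol set admits unscheduled visits and is limited to completers.

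**A tempting stronger reading.** A reader might infer that the mapping was made with interim results by treated eye in hand, because Protocol 11.5.7 plans analyses at Years 3 and 4 and Protocol 7.1 says "The approximate study end date is planned to be towards the end of year 2022". The documents do not support this. These are planned dates only, SAP Version 2.0 still describes the interim analyses as planned, and nothing says who saw any results.

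**Conclusion.** The concern holds as a gap in the written method. The visible SAP names a decision-maker for the analysed BCVA visit, but gives no rule for choosing among available visits and states no masking for that choice. It does not follow that the reviewers were unmasked or that any result is biased; the documents show neither.

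The size depends on how many patients have a second candidate value. At about 10%, even a choice always made in favour of GS010 leaves type I error near nominal (0.050 to 0.065) and shifts the mean by less than 1 letter. At 25%, with the visit chosen on the between-eye difference, it is at most about 0.14 (EMA) or 0.09 (FDA) within the assumed ranges, with a shift of 1 to 2 letters against a 15-letter responder threshold. The upper figures rest on n = 76 and 50% visit noise, neither of which the documents support or exclude. The primary safety analysis is unaffected.

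Severity: minor to should-fix.

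**What to change.** In SAP 5.5.1, replace the discretionary review with a programmed rule that uses only visit dates and visit type and applies identically to both eyes:

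1. Use the scheduled visit for its own time point, and state whether one outside its window is accepted.
2. If it is absent, use the unscheduled or early termination visit nearest the target date within a pre-stated window (for example, the schedule's plus or minus 4 weeks), with ties going to the earlier visit.
3. Otherwise apply LOCF. Earlier scheduled values may be carried forward; state whether unscheduled or early termination values from outside the window may be carried too.
4. Keep the existing Year 2 fallback to Week 96.

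List every difference between this rule and the 30 June 2022 mapping, and present results under both, since the rule would itself come after that mapping. Report by visit how many subjects had more than one candidate and how many were carried forward; those counts would show whether the issue is material.

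If a value-blind rule and a masked review already exist, in the mapping file or the data review meeting, stating them in 5.5.1 is enough.

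The cost is SAP wording, a short program and one listing. The downside is that a few values the sponsor would have accepted may move to LOCF; the count by visit makes that visible.

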8.2 Schedule of Events

The Schedule of Events (**Table 1**) provides the procedures/assessments to be performed at each scheduled visit for long-term follow-up period.

The inclusion assessments may be performed at the Week 96/EOS visit of RESCUE/REVERSE and up to 1 day prior to the Visit 2 (Year 2.5 visit [up to 180 days post Week 96]).

Table 1: Schedule of Events

Years post-treatment	Inclusion Period	Long-term Follow-up Period			
	Year 2 (Week 96) ^a	Year 2.5 (± 4 weeks)	Year 3 (± 4 weeks)	Year 4 (± 4 weeks)	Year 5 EOS (± 4 weeks) ^b
Procedure	Visit 1	Visit 2	Visit 3	Visit 4	Visit 5
Informed consent	X				
Clinical Assessments/Procedures					
Review inclusion/exclusion criteria	X				
Medical history	X				
Physical examination including vital signs ^c	X				X
Electrocardiogram (12-lead)	X				X
Review concomitant medications	X	X	X	X	X
Adverse events/serious adverse events ^d	X	X	X	X	X
Laboratory Assessments					
Hematology/serum chemistry including liver function ^e	X				X
Quality of Life Assessments					
VFQ-25 ^f	X		X	X	X
SF-36 ^f	X		X	X	X
Ocular and Vision Assessments					
Slit-lamp examination ^g	X	X	X	X	X
Goldmann applanation tonometry for intraocular pressure ^h	X	X	X	X	X
Refraction for BCVA	X	X	X	X	X
Visual Acuity (ETDRS)	X	X	X	X	X
Humphrey TM visual field 30-2	X	X	X	X	X
Pelli-Robson contrast sensitivity ^h	X		X	X	X
SD-OCT	X	X	X	X	X
Color fundus photography	X	X	X	X	X

Abbreviations: BCVA, best-corrected visual acuity; EOS, End of Study; ETDRS, Early Treatment Diabetic Retinopathy Study; SD-OCT, spectral domain optical coherence tomography; SF-36v2, 36-item Short Form Health Survey; VFQ-25, Visual Function Questionnaire-25, version 2.

^a The inclusion window will be from Week 96 visit up to 1 day prior to Visit 2, which will be approximately 180 days post W96/EOS.

^b Subjects who discontinue participation in the long-term follow-up study prematurely (i.e., prior to Visit 5) will complete an EOS visit, including Visit 5 procedures.

- ^c Examination includes general appearance, skin, head, eyes, ears, nose, throat, neck, thyroid, chest/lungs, heart, abdomen, lymph nodes, extremities, and body weight and height. Vital signs include temperature, pulse rate, and systolic and diastolic blood pressure.

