8.3 Visit 1: Inclusion Period (Year 2)

The Inclusion Period will start on the date of the last visit (W96) of the RESCUE/REVERSE study and end 1 day prior to Visit 2 (Year 2.5, Day 179) of the long-term follow-up study.

Ideally, the Visit 1 should be combined with the Week 96/EOS visit of RESCUE/REVERSE. If this is not possible, a separate Visit 1 will be scheduled during the Inclusion Period to sign the informed consent, review eligibility criteria, review AEs/SAEs and concomitant medications, and perform any additional assessments that were not completed during the Week 96/EOS visit of RESCUE/REVERSE.

The following assessments will be performed during the Inclusion Period in the approximate order listed:

- Review and update medical, surgical, and prior medication history
- Physical examination and vital signs
- Review of inclusion/exclusion criteria
- Review concomitant medication
- AEs/SAEs
- Clinical laboratory testing (hematology and serum chemistry including liver function)
- ECG
- VFQ-25 questionnaire
- SF-36v2 questionnaire
- Ocular and vision assessments
 - Refraction for BCVA, performed prior to pupil dilation
 - Visual acuity assessment, performed prior to pupil dilation
 - HVF 30-2, performed prior to pupil dilation
 - Goldmann applanation tonometry for intraocular pressure (IOP) measurement, performed prior to pupil dilation
 - Pelli-Robson contrast sensitivity, performed prior to pupil dilation
 - Slit-lamp examination (SLE) performed pre- and post-pupil dilation
 - SD-OCT, performed after pupil dilation

- Color fundus photography after pupil dilation.

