3.2 DURATION AND SCHEDULE OF STUDY PARTICIPATION

Study Duration

Total study follow-up is 3 years and the study will end with the last subject's last visit. The estimated total length of the subject follow-up is 5 years after the initial IMP administration.

Study Schedule

The follow-up study is divided into the following visits:

Visit 1: Inclusion Period (Year 2)

The Inclusion Period starts on the date of last visit (Week 96) of the RESCUE/REVERSE study and ends 1 day prior to Visit 2 (Year 2.5, Day 180 post Week 96 (Visit 12 of CLIN-03)) of the long-term follow-up study.

It is preferable for Visit 1 to be combined with Week 96/EOS visit of RESCUE/REVERSE study, but if not possible this can be a separate visit during the Inclusion Period. During this Period the informed consent is signed, eligibility criteria, adverse events (AEs)/ serious adverse events (SAEs) and concomitant medications (CMs) are reviewed and any other assessments needed that were not performed during the Week 96/EOS visit of RESCUE/REVERSE are completed.

Physical examinations including vital signs, electrocardiogram, laboratory assessments, quality of life, and ocular and vision assessments will also be done. A review of medical, surgical and prior medication history will also be performed.

Visit 2: Year 2.5 (\pm 4 Weeks) Post-treatment

During this visit, concomitant medications are reviewed, along with AEs and SAEs, and Ocular and Vision Assessments are carried out.

Visit 3: Year 3 (\pm 4 Weeks) Post-treatment

During this visit, assessments from Visit 2 are repeated and additional quality-of-life and Pelli-Robson contrast sensitivity assessments are carried out.

Visit 4: Year 4 (\pm 4 Weeks) Post-treatment

All assessments from Visit 3 are repeated during this visit.

Visit 5: Year 5 (\pm 4 Weeks) Post-treatment (EOS) or Early Termination Visit (ETV)

Assessments from Visit 4 are repeated. Additional physical examination including vital signs, electrocardiogram, and laboratory assessments, are performed.

Unscheduled Visit

Unscheduled visits can be performed anytime to assess or monitor AEs, or at the subject's or investigator's request. The date and reason for the unscheduled visit should be recorded in the source documents.

The study plan and assessments are shown in Protocol Section 8.2, Table 1: Schedule of Events of the protocol.

Sponsor: GenSight Biologics
 Protocol No: GS-LHON-CLIN-06

Statistical Analysis Plan
 Final Version 2.0 / 30-June-2022

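### SAP 5.5.1 ranks the CLIN-06 inclusion value above Week 96 for Year 2 with no date limit, so a late value can displace a correctly timed one

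*SAP*

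**What the plan says.** **Timing of Visit 1.** The Schedule of Events (Protocol 8.2, repeated in SAP 3.2) heads Visit 1 as Year 2 (Week 96). Visits 2 to 5 each carry a window of ±4 weeks; Visit 1 carries none. The table footnote reads "The inclusion window will be from Week 96 visit up to 1 day prior to Visit 2". Protocol 7.1 prefers that the assessments be done at the Week 96/EOS visit, but otherwise "the assessments may be performed at a later date during the Inclusion Period, but no later than one day before the Year 2.5 visit".

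**Content of a separate Visit 1.** Protocol 8.3 reserves it for consent, eligibility, adverse events, concomitant medication and whatever was not completed at Week 96. SAP 3.2 says the same, but then lists ocular and vision tests among the Visit 1 procedures. The Schedule of Events marks every vision assessment at Visit 1.

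**Choice of the Year 2 value.** SAP 5.5.1 gives two rules. First, the sponsor reviews the visits that have a BCVA value "to decide, for each patient, which visit will be used for this specific timepoint analysis". Second, "If Year-2 visit is not available at Clin06 inclusion, then" Follow-up Visit 12 of the parent study (Week 96) is used. Neither rule carries a date condition.

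**Use.** Years 2 and 2.5 are separate time points for LogMAR (SAP 8.5.2.2), SD-OCT (8.5.2.3), responders (8.5.2.4) and HVF (4.3).

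**The concern.** The enrolment deadline doubles as the assessment window for the first efficacy time point. On its own that would matter little, because the parent studies supply a Week 96 value. The order of precedence is what creates the problem: Week 96 is used only when the inclusion visit is unavailable, however late that visit was.

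Protocol 5.3 gives the purpose of further observation as learning whether efficacy is sustained, declines or needs more time. Year 2 is the first point on that curve. If some Year 2 values were in fact taken close to Year 2.5, the early part of the curve is blurred, and only for subjects assessed late, who are not a random subset. In the exploratory repeated-measures model (SAP 8.7.1), an AR(1) structure indexed by visit would treat a 1-day gap and a 180-day gap as the same lag.

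**Working it through.** Days below are elapsed days since injection; study days under SAP 5.1 are one higher.

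**1. The plan's own figure.** Protocol 8.2 puts Visit 1 "up to 1 day prior to Visit 2, which will be approximately 180 days post W96/EOS". The last inclusion day is therefore 180 − 1 = 179 days after Week 96. This agrees with Protocol 8.3, which has the period "end 1 day prior to Visit 2 (Year 2.5, Day 179) of the long-term follow-up study". SAP 3.2 attaches Day 180 to the same phrase. The two are compatible if Day 179 is the last inclusion day and Day 180 is Visit 2, but the wording should be aligned.

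**2. Converted to time since injection.**
- Week 96: 96 × 7 = day 672; 672 / 365.25 = 1.84 years.
- Last inclusion day: 672 + 179 = day 851; 851 / 365.25 = 2.33 years.
- Visit 2 on the Day 180 anchor: 672 + 180 = day 852.
- Smallest Year 2 to Year 2.5 gap under the current rule: 852 − 851 = 1 day.
- Gap if Week 96 is used: 852 − 672 = 180 days, or 152 to 208 days if ±28 days is applied around Day 180.

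**3. Sensitivity to the anchor.**
- With calendar years, Year 2.5 is 2.5 × 365.25 = day 913.1, and its window is days 885.1 to 941.1. Day 852 falls outside. A fixed Day 179 cap would then leave at least 885.1 − 851 = about 34 days, but the limit of one day before Visit 2 still permits 1 day.
- With 48-week years (Week 96 = Year 2), Year 2.5 is 2.5 × 336 = day 840, and its window is days 812 to 868. This contains day 852, so the 1-day gap stands.

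The mismatch between Day 180 after Week 96 and calendar Year 2.5 is a separate inconsistency to reconcile.

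**4. When the rule does harm.**

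| Situation | Year 2 value under SAP 5.5.1 | Effect |
|---|---|---|
| Visit 1 combined with Week 96 | The same measurement | None |
| Late consent, tested at Week 96, not retested | Week 96 by fallback | None, if availability is judged per endpoint |
| Tested at Week 96 and again at a late Visit 1 | Late value | Displaces a correctly timed value |
| Not tested at Week 96, tested at a late Visit 1 | Late value | Mistimed, but no better value exists |

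**5. Which endpoints.** The Schedule of Events has BCVA, HVF and SD-OCT at both Visit 1 and Visit 2, so for these the two time points can nearly coincide. Pelli-Robson, VFQ-25 and SF-36 are done at Visit 1 but not at Visit 2, so a late Year 2 value is mistimed without colliding with a Year 2.5 value.

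**The case against.** The strongest reply is that the plan already handles this. Protocol 8.3 confines a separate Visit 1 to tests missed at Week 96, so duplicates should be uncommon, and without a duplicate the fallback delivers Week 96. For BCVA, the sponsor's patient-by-patient review may choose the better-timed visit. Efficacy is secondary (SAP 8.5.4), change is measured from pre-treatment baseline (SAP 5.2 and 5.3), and no test of Year 2 against Year 2.5 is specified.

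Much of this stands, and it limits the point. It does not remove it. The Schedule of Events and SAP 3.2 still list the vision tests at Visit 1, so retesting is not ruled out. The review is framed around visits with a BCVA value, states no date rule, and does not say how HVF or SD-OCT values are chosen.

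A reader might infer more than the documents support:
- *Every late consenter has a mistimed Year 2 value.* Not so: those tested at Week 96 and not retested receive their Week 96 value.
- *The GS010 versus sham comparison is biased.* This is not shown. The EMA comparison is within subject, so if both eyes are tested at the same visit, lateness applies to both. Nothing in the documents suggests that lateness depends on which eye was treated.
- *The loss of spacing is 241 days.* That compares day 672 with a calendar Year 2.5 at day 913. The documents place Visit 2 about 180 days after Week 96.
- *Contrast sensitivity and quality of life are merged across time points.* They cannot be, since neither is collected at Visit 2.
- *Durability to Years 3 to 5 is undermined.* Those results do not depend on the Year 2 label.

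**Conclusion.** The point holds and is minor. SAP 5.5.1 allows a value taken as late as about day 851 (2.33 years) to be analysed as Year 2 in preference to an existing Week 96 value. For BCVA, HVF and SD-OCT, the Year 2 to Year 2.5 spacing can fall from about 180 days to 1 day. This is a worst case per subject. The documents give no count of subjects with late or duplicate assessments, and Protocol 8.3 makes a small number likely.

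The conclusion rests on three assumptions: that the SAP 5.5.1 fallback means what it says for every endpoint; that the sponsor's visit review applies no unwritten date rule; and that no visit-window rule sits in the part of the SAP between 5.5.2 and 6, which was not in the text reviewed. SAP 6.3 mentions an allowable time window without defining it, so such a rule cannot be excluded.

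**What to change.** Reverse the precedence in SAP 5.5.1, for example: *The RESCUE/REVERSE Week 96 (Follow-up Visit 12) value is the Year 2 value for every subject and endpoint that has one. The CLIN-06 Visit 1 value is used only where the Week 96 value is missing.* Apply the same rule in the BCVA visit review and check the existing selection listing against it.

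Where the only value is late, keep it and report its actual study day. As a sensitivity analysis, repeat the Year 2 summary without values taken more than 4 weeks after the Year 2 anchor, and state the anchor: Week 96 gives 672 + 28 = day 700, calendar Year 2 gives 730 + 28 = day 758. Such values should not be dropped from the main analysis. Doing so would trigger LOCF under SAP 5.5.1 and 6.2, replacing an observed value with an older one.

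Changing the Visit 1 window in Protocol 8.2 would achieve nothing now, because SAP 3.1 describes enrolment as past.

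The cost is a short SAP edit, a small programming change and one extra sensitivity table. Protocol 11.1 already provides for importing the parent-study data needed for the analyses.
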